6.2. Immunogenicity Analyses

The incidence of antibodies to sirukumab will be summarized for all subjects who received at least 1 administration of sirukumab and have appropriate samples for detection of antibodies to sirukumab (ie, subjects with at least 1 sample obtained after sirukumab treatment).

7. SAFETY

7.1. Adverse Events

Adverse events (AEs) are coded using the MedDRA dictionary (version 17.0 or above). Treatment-emergent adverse events (TEAEs) that occurred in the double-blind phase will be summarized by system organ class, preferred term, and treatment group. Adverse events that occurred in the follow up phase will be summarized separately.

Adverse events in different phases of the study are defined as below:

- Treatment-emergent adverse events during the double-blind phase are defined as AEs with an onset during the double-blind phase. In other words, treatment-emergent AE during the double-blind phase should satisfy the condition: Double-blind start date/time ≤ AE onset date/time ≤ double-blind end date. If onset time is missing and AE onset date/time is the same as the double-blind start date/time, the AE is defined to be treatment emergent in the double-blind phase.
- Adverse events during the follow up phase are defined as AEs with an onset during the follow up phase. AEs during the follow up phase should satisfy the condition: (follow up phase start date \leq AE onset date/time and AE onset date \leq follow up phase end date).

A TEAE is an event that is new in onset or increased in severity following treatment initiation. An event that starts prior to, and ends after the initiation of study medication will be considered treatment-emergent only if the severity increases after the start of medication. Adverse events will not be considered treatment-emergent if they occur or increase in severity during the follow up phase. Adverse events occurring during the follow up phase will be summarized separately. In addition, AEs will be summarized by severity and relationship to study drug using the preferred term. For the summaries of AEs by severity/relationship to study drug, the observation with the most severe occurrence/closest relationship to study drug will be chosen if there is more than one incident of an adverse event reported during the analysis phase by the subject.

Serious AEs (SAEs) and AEs that lead to study discontinuation will be summarized separately by treatment group, system organ class, and preferred term. Data listings will also be generated for deaths, other SAEs, and discontinuations due to AEs.

Adverse Events of Special Interest

Clinically relevant TEAEs of special interest will be examined in malignancies, active TB, hepatobiliary abnormalities (as defined in the protocol), and gastrointestinal perforations.

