2.7. Incomplete/Missing Dates for Adverse Events

Treatment-emergent adverse events (AEs) for DB phase are those events with an onset date on or after the start of double-blind study medication, and occurred on or before the end of the double-blind phase. A conservative approach will be used to handle the missing dates for adverse events.

The rules for estimating incomplete AE onset dates will be as follows:

(1) The missing day of the month will be estimated as follows: If the month and year are known and double-blind study medication started during that month then the estimated date is the start date of double-blind study medication. If the month and year are known and double-blind study medication started prior to that month then the estimated date is the 1st day of the month. If the month and year are known and double-blind study medication started are known and double-blind study medication are known and double-blind study medication started prior to that month then the estimated date is the 1st day of the month. If the month and year are known and double-blind study medication started after the month, then no estimation will be done, and the AE will not be considered as treatment emergent for the double-blind phase.

(2) If both the day and the month are missing: No estimation will be performed. However, these AEs will be considered treatment emergent for the double-blind phase and will be included in the double-blind treatment summaries, except for the calculation of duration of the AE. Attempts will be made to get at least the month for the adverse events.

For incomplete AE resolution dates, the rules are:

- (1) The missing day of the month will be estimated as follows: If the month and year are known and the study medication was stopped before, or during that month, the estimated date is the last day of the month or the end of the doubleblind phase, whichever is earlier. If the study medication stopped after that month then the estimated date is the last day of the month.
- (2) If both the day and the month are missing: the estimated resolution date is the end of the double-blind phase.

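### The SAP's TEAE phase condition uses onset date alone and contradicts its own worsening rule; the follow-up condition gives worsening in follow-up no place in a summary

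*SAP*

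**What the plan says.** SAP section 7.1 defines a TEAE in two ways.

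- **Phase rule (bullet).** "Treatment-emergent adverse events during the double-blind phase are defined as AEs with an onset during the double-blind phase". The bullet then turns this into a condition to be satisfied: "Double-blind start date/time ≤ AE onset date/time ≤ double-blind end date". Severity plays no part.
- **General rule (paragraph below the bullets).** "A TEAE is an event that is new in onset or increased in severity following treatment initiation". An event that is already present at the start of medication and continues past it "will be considered treatment-emergent only if the severity increases after the start of medication".

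Section 2.7, on incomplete AE dates, describes double-blind TEAEs as "those events with an onset date on or after the start of double-blind study medication", up to the end of that phase, and has no worsening clause. Where the onset month is known and falls before the month of first dose, 2.7 rules the event out as treatment-emergent, again with no exception for worsening.

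For follow-up, 7.1 states: "Adverse events during the follow up phase are defined as AEs with an onset during the follow up phase". It adds: "Adverse events will not be considered treatment-emergent if they occur or increase in severity during the follow up phase". The only destination it gives is: "Adverse events occurring during the follow up phase will be summarized separately".

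**The concern.** A programmer who codes the stated date condition and one who codes the paragraph below it would both be following section 7.1, yet they would produce different TEAE tables. Under the date condition, a condition present before the first dose that worsens on study drug drops out of the TEAE incidence and severity summaries.

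In follow-up the difficulty is a gap, not a contradiction. Worsening in that phase is barred from creating a TEAE, and the follow-up class admits only events with onset in that phase.

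Overall safety and tolerability is the first secondary objective in section 1.1. Follow-up lasts 14 weeks against 12 weeks of double-blind treatment (section 1.2). Under section 2.3.1 the double-blind phase can end at early termination, and follow-up starts the next day. For a subject who stops early, any later worsening therefore falls under the follow-up rule.

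**Working it through.** The SAP gives no figure to reproduce and no arithmetic applies. The check applies the written rules of 2.7 and 7.1 to each combination of onset phase and worsening phase, taking each event as one record with one onset date.

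| Case | Onset | Severity increases | Date condition (7.1 bullet, 2.7) | Paragraph in 7.1 | Follow-up rule | Result |
|---|---|---|---|---|---|---|
| 1 | Before first dose | Double-blind | Not a TEAE | TEAE | Not met | Contradiction |
| 2 | Before first dose | Follow-up only | Not a TEAE | Not a TEAE | Not met | In neither summary |
| 3 | Double-blind | Follow-up | TEAE | TEAE by onset, but see below | Not met | Worsening in no follow-up summary |
| 4 | Double-blind | None later | TEAE | TEAE | Not met | Consistent |
| 5 | Follow-up | Any | Not a TEAE | Not a TEAE | Met | Consistent |

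**Case 1.** The paragraph concerns an event that starts before medication, so its onset date precedes the double-blind start. The lower bound of the date condition therefore always fails. No event of this kind can satisfy both rules.

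**Case 2.** The onset is too early for either phase condition, and the paragraph withholds TEAE status because the worsening falls in follow-up. No AE summary defined by phase takes the event.

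**Case 3.** The event is tabulated in the double-blind phase by its onset. Its later worsening does not qualify for follow-up because the onset was earlier. The sentence on follow-up also names occurrence and increase in severity as separate cases, but the sentence after it sends only the first to a summary. Read literally, the sentence on follow-up could also be taken to withdraw TEAE status from this event. The likelier intention is that worsening in follow-up does not create that status, but the text does not say so.

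**Cases 4 and 5** show that the rules work where worsening plays no part. The defect is confined to worsening across a phase boundary.

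**The case against.** **The intended rule is already there.** Section 7.1 states the worsening rule plainly one paragraph after the bullets. The bullets can be read as assigning events to phases and the paragraph as completing the definition. That is a fair reading of the intention, and nobody should conclude that the plan has no worsening rule. But the bullet is worded as a definition with a condition to be met, and 2.7 repeats the onset-only form, so the text needs aligning.

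**Section 2.7 is only about missing dates.** This is largely true, and its opening sentence is weak evidence on its own. It still excludes pre-treatment onset with no exception for worsening, so it should carry the same definition.

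**Events are not lost altogether.** A reader might infer that a Case 2 event appears in no AE table at all. The SAP does not support that. The summaries of serious events and of events leading to discontinuation, and the listings of deaths, other serious events and discontinuations due to AEs, are not limited by onset phase. What the rules lose is the entry in the TEAE or follow-up AE summary. That matters most for an event that is not serious and does not lead to discontinuation.

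**The follow-up treatment is partly a choice.** Keeping follow-up worsening out of the TEAE class is deliberate and defensible. What does not follow from that choice is leaving the worsening without a follow-up summary. If the eCRF keeps one record at maximum severity, a Case 3 event would show its worse grade in the double-blind severity table. The grade would then be reported, but under the wrong phase.

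**It depends on how worsening is recorded.** This objection stands. If each worsening is a new record with its own onset date, the onset conditions capture it. Section 7.1 does foresee more than one incident of an event within a phase, which is compatible with that practice but does not establish it. The wording about an event that starts before medication and ends after it suggests a change within one record.

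**Conclusion.** The point holds as a contradiction within section 7.1 (with 2.7 on the onset-only side) and a gap in the follow-up rule. It deserves correction before the safety tables are programmed, but it is not a major threat to the safety assessment.

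The number of affected events cannot be derived from the SAP. It is zero if every worsening is entered as a new AE record with its own onset date. Otherwise it is unknown and probably small. One might say that every worsening event kept under its earlier onset date fails the date condition. That is true, but it only restates the definition. It estimates neither a number of events nor a difference between arms, and the SAP supports no such estimate.

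The conclusion rests on reading the conditions as written and on one record per event. AE recording conventions may be set out in the protocol or eCRF instructions, which were not available.

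**What to change.** - Use one TEAE definition in both 2.7 and 7.1: onset in the double-blind phase, or earlier onset with an increase in severity during the double-blind phase. The 2.7 rule for partial onset dates before first dose should defer to it.
- Define follow-up AEs as those with onset, or an increase in severity, during follow-up.
- State that worsening in follow-up does not remove TEAE status from an event with double-blind onset.
- Base the derivation on the date of worsening or on the new AE record, whichever the eCRF provides, and say which. The SAP does not show that a worsening date is collected, so this must be checked before programming.

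The cost is about two sentences and one derivation. AE counts would rise slightly, and no efficacy analysis is touched.

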1.1. Trial Objectives

Primary Objective

To evaluate the efficacy of sirukumab as adjunctive treatment to antidepressant therapy (monoaminergic antidepressant) where sirukumab (administered as a 50mg subcutaneous (SC) injection at Day 1, Day 28 and Day 56 during the 12-week double-blind treatment period) is compared to adjunctive placebo based on the change from baseline to 12-week endpoint in depressive symptoms as measured by the total score on the Hamilton Depression Rating Scale (HDRS₁₇), in subjects diagnosed with Major Depressive Disorder (MDD) who have had a suboptimal response to the current standard oral antidepressant therapy and have a screening high sensitivity C-Reactive Protein (hsCRP) \geq 0.300 mg/dL (International System of Units (SI) 3.00 mg/L).

Secondary Objectives

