1.2. Trial Design

This is a multicenter, double-blind, placebo-controlled study in male and female subjects, 21 to 64 years of age inclusive, with major depressive disorder (MDD) who have had a suboptimal response to standard oral antidepressant therapy; have failed no more than 3 antidepressant treatments in the current major depressive episode.

The study will consist of 3 phases: a screening phase of up to 4 weeks, a 12-week doubleblind treatment phase, and a 14-week posttreatment follow-up phase. The total duration of subject participation will be approximately 26 weeks.

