2.3.1. Analysis Phase Start and End Dates

Double-Blind Phase

The analysis reference start date of the DB analysis phase is the date of the first dose of DB medication. The analysis reference end date of the DB analysis phase is the maximum of date of the last visit in the DB treatment phase or date of early termination from DB phase. For randomized subjects who did not receive any medication in the DB phase, the reference start date is missing.

Follow-Up Phase

The analysis reference start date of the Follow-up (Post-treatment) analysis phase is the day after the end of DB. The analysis reference end date is the maximum of the last follow-up visit date and end of trial date.

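### SAP 7.1 reviews events of special interest only as double-blind TEAEs, so those with onset in follow-up (14 of 26 planned weeks) are left out of the targeted review

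*SAP*

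**What the plan says.** The special-interest paragraph at the end of SAP Section 7.1 reads: "Clinically relevant TEAEs of special interest will be examined in malignancies, active TB, hepatobiliary abnormalities", with gastrointestinal perforations as the fourth category. It refers to the protocol only for the definition of hepatobiliary abnormalities. It names no table and no phase other than the one implied by the term TEAE.

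Section 7.1 sets the TEAE window as "Double-blind start date/time ≤ AE onset date/time ≤ double-blind end date" and adds: "Adverse events will not be considered treatment-emergent if they occur or increase in severity during the follow up phase". Section 2.3.1 ends the double-blind phase at the "maximum of date of the last visit in the DB treatment phase or date of early termination from DB phase". It then says: "The analysis reference start date of the Follow-up (Post-treatment) analysis phase is the day after the end of DB".

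Section 1.2 plans a 12-week double-blind phase and "a 14-week posttreatment follow-up phase".

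Three other provisions matter. Section 7.1 has follow-up AEs summarised separately. It also plans SAE summaries by treatment group and listings of deaths and other SAEs, with no phase limit stated. Section 2.5.5 restricts the Safety (FU) set to subjects with at least one visit in the follow-up phase.

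**The concern.** A special-interest analysis gathers under one heading events that would otherwise be spread over several preferred terms, so that a small number of related cases can be seen together by arm. As Section 7.1 is written, that gathering stops when the double-blind phase stops, although observation continues for longer than the double-blind phase itself lasted. The SAP does not treat follow-up as outside its safety interest: Sections 7.2 and 7.3 give descriptive statistics for laboratory tests and vital signs in both phases.

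With about 192 subjects and event types that may produce very few cases, one or two events can change the picture by arm. If some of them begin in follow-up, a reader of the targeted review would not see them there and would have to rebuild the category from general outputs.

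**Working it through.** **Step 1. Does the rule exclude follow-up events?** Set the provisions side by side.
- Section 7.1: only TEAEs enter the special-interest review.
- Section 7.1: a TEAE needs onset no later than the double-blind end date, and events arising or worsening in follow-up are expressly not TEAEs.
- Section 2.3.1: the double-blind phase ends at the later of the last double-blind visit and early termination; follow-up starts the next day.

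An event with a known onset date in follow-up therefore cannot enter the review. The only exceptions are events with incomplete onset dates that the conservative rules in Section 2.7 assign to the double-blind phase.

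**Step 2. How much planned time is excluded?**
- Inputs: double-blind phase 12 weeks, follow-up 14 weeks (Section 1.2).
- Check against the SAP's own figure: 12 + 14 = 26 weeks, which agrees with "The total duration of subject participation will be approximately 26 weeks" if screening is not counted.
- Share excluded by Section 1.2: 14 / 26 = 0.538, or 54%.
- Share excluded by Table 1, where Week 12 has target Day 84 and the last follow-up visit, Week 22, has target Day 154: (154 − 84) / 7 = 10 weeks, and 10 / 22 = 0.455, or 45%.
- In subject-time, as an upper bound with all 192 subjects (Section 1.4) followed for the full Section 1.2 durations: double-blind 192 × 12 / 52 = 44.3 person-years; follow-up 192 × 14 / 52 = 51.7 person-years; total 96.0.

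**Step 3. Where do the excluded events go?**

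| Event with onset in follow-up | Special-interest review | General follow-up AE summary | SAE summaries and listings |
|---|---|---|---|
| Serious, subject has a follow-up visit | No | Yes | Yes |
| Serious, subject has no follow-up visit | No | No | Yes |
| Non-serious, subject has a follow-up visit | No | Yes | No |
| Non-serious, subject has no follow-up visit | No | No | No |

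The second and fourth rows follow from the one-visit requirement of the Safety (FU) set in Section 2.5.5. The fourth row concerns an event recorded after early termination in a subject who never attended a follow-up visit. None of the general outputs groups events by special-interest category.

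**Step 4. Completers and early terminators.** Section 1.1 plans an "injection at Day 1, Day 28 and Day 56 during the 12-week double-blind treatment period". For a completer, the window from Day 56 to the Week 12 target of Day 84 covers 84 − 56 = 28 days after the last dose. For an early terminator the window can close sooner after a dose, and later events pass to follow-up.

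**The case against.** The strongest objection is that nothing is lost. The SAP uses a phase-based TEAE definition consistently (Sections 2.7 and 7.1), summarises follow-up AEs separately and defines an analysis set for them. Its SAE outputs have no phase limit, so a malignancy, active TB or perforation that meets the seriousness criteria would appear there by arm. With few events, a reader could find them in a listing. The protocol is not shown and may set special-interest reporting for the whole study.

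Most of this stands as a limit on the point. A reader might infer that follow-up special-interest events go unreported; the documents do not support that. What remains is that they are not grouped by category, and that the non-serious case in the last row of the table reaches no AE summary. The possible protocol provision cannot be checked, but the restriction to TEAEs is the SAP's own statement and not something it leaves to the protocol.

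Three further inferences are tempting and should not be drawn.
- That about half the special-interest events are missed. This needs a constant event rate, and the SAP gives no rate or latency.
- That 48 of 192 subjects have a shortened window. The 25% dropout in Section 1.4 is a planning assumption for the 142 subjects with screening hsCRP of at least 3.00 mg/L, where it gives 0.25 × 142 = 35.5, about 36. Applying it to all 192 is an extrapolation.
- That the TEAE window should run one dosing interval past the last dose. The SAP contains no pharmacokinetic basis for that length, and completers already have 28 days.

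It is also fair to say that Section 7.1 promises only that these events will be examined; it does not describe a by-arm comparison that would then be biased.

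**Conclusion.** The point holds as a limit on the scope of the special-interest review. By the SAP's own definitions, special-interest events with onset in follow-up are excluded from it for 14 of 26 planned weeks after first dose (54%), or 10 of 22 weeks (45%) by Table 1. Both figures are shares of planned time under full participation. The number of events affected cannot be computed from the document.

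The consequence is incomplete grouping, with a narrow true gap for non-serious events after early termination in subjects with no follow-up visit. The conclusion assumes that the SAE outputs cover both phases, as their wording allows, and that no protocol provision widens the review.

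**What to change.** In Section 7.1, replace the restriction to TEAEs in the special-interest paragraph with a statement that malignancies, active TB, hepatobiliary abnormalities and gastrointestinal perforations will be tabulated by category and treatment group for the double-blind phase, for the follow-up phase, and for both combined from first dose to end of trial. State that the denominator is all treated subjects, that is, the safety analysis set and not the Safety (FU) set, so that subjects without a follow-up visit are included.

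The general TEAE definition can stay as it is. The combined column already covers early terminators, so no separate extension of their window is needed. The cost is a change of SAP wording and one extra descriptive table on data already collected; no test, sample size or trial procedure is affected.

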7.2. Clinical Laboratory Tests

Descriptive statistics (N, mean, median and range) for values and changes from baseline will be provided for clinical laboratory tests (hsCRP, hematology, chemistry, lipid panel [fasting] and urinalysis) at each scheduled time point in the double-blind and follow up phases

In addition, shift table from baseline to post-baseline values with respect to the normal range will be provided.

